6.2. Study Conduct

6.2.1. Accrual

The number of patients accrued will be summarized by country and investigational site on All Enrolled Population. A by-patient listing of accrual with cohort, first dosing date, country and investigational site will also be presented.

6.2.2. Protocol Deviations

Important protocol deviation (ICH E3 Q&A (R1)) is defined as a subset of protocol deviations that may significantly impact the completeness, accuracy, and/or reliability of the study data or that may significantly affect the subject's rights, safety or well-being. These include: Important ICF issues, inclusion/exclusion criteria not met, withdrawal criteria not followed; wrong treatment, incorrect dose/overdose based on protocol definitions, important deviations based on protocol design, and other important GCP deviations.

Important protocol deviations will be summarized by category and listed as well.

6.3. Study Population

6.3.1. Patient Disposition

The number of patients in each study population (All Enrolled Population, All Treated Population, Response Evaluable Set, Pharmacodynamic Evaluable Set) will be summarized by cohort. Patient disposition table will include number of patients treated at data cutoff, number of subjects with treatment ongoing at data cutoff, number of discontinued patients along with the reason for study discontinuation.

For Cohort 4 only, the number and percentage of patients in DLT Evaluable Set will be presented by different dosage levels of TAS-120. The reasons for exclusion will be summarized as well.

6.3.2. Demographic and Other Baseline Characteristics

The following baseline characteristics will be summarized by cohort. Listings will also be provided.

- Age (descriptive statistics)
- Age category ($< 65, \ge 65$)
- Sex (Male, Female)
- Ethnicity (Hispanic/Latino, Not Hispanic/Latino)
- Race (Caucasian/white, Black, Asian, American Indian or Alaska Native, Native Hawaiian or Other Pacific Islander, Other)
- Region (North America, Europe)
- ECOG PS (0, 1)
- Baseline height
- Baseline weight
- Prior surgery (Yes/No)
- Prior radiotherapy (Yes/No)
- Prior systemic anticancer therapy (Yes/No)
- Number of prior lines of systemic therapy
- Breast cancer type (HR⁺HER⁻, TNBC) (for Cohort 3)
- FGFR amplification status by local lab and/or central lab

All collected information for cancer diagnosis will be summarized and listed.

6.3.3. Medical History

Medical history will be coded according to the Medical Dictionary for Regulatory Activities (the most up-to-date version at the time of analysis). Medical history will be summarized by system organ class and preferred term for each cohort and for all patients and will be listed as well.

6.3.4. Prior/Concomitant Therapy

6.3.4.1. Prior Anticancer Therapy

Prior anticancer surgery and prior radiation therapy will be summarized for each cohort and for all patients based on All Treated Population. For prior surgery, the number and percentage of patients with at least one anticancer surgery for primary disease will be presented. The type of surgery will be summarized. The time from prior surgery to the first dosing date will be summarized. For prior radiation therapy, the number and percentage of patients with at least one radiation therapy for primary disease will be presented. The intention of radiotherapy, radiation therapy site location, duration of radiation therapy and time from end date of radiation therapy to first dosing date will be summarized.

For prior anticancer therapy, the number and percentage of patients with at least one prior anticancer therapy for primary disease will be presented. The treatment type and therapy type will be summarized. Patients' best response (CR, PR, SD, PD, NE) to the therapy will be summarized. The duration of anticancer therapy and time from end date of anticancer therapy to first dosing date will be summarized. The reason for therapy discontinuation will also be summarized. The above analysis will be repeated for each treatment type (adjuvant therapies, neoadjuvant therapies, therapies for advanced/metastatic disease) in separate tables.

Prior anticancer therapy will be coded with World Health Organization (WHO) Drug Dictionary (most up-to-date version at the time of analysis) and will be summarized by ATC level 2 (Therapeutic Main Group) and ATC level 4 (Chemical/Therapeutic Subgroup) for each cohort and for all patients based on All Treated Population. Medications and therapies will be sorted in descending order of frequency of ATC level 2 and ATC level 4 within ATC level 2 in the total column. A patient will be counted only once within each level of summarization if the patient has taken a medication more than once.

All collected information for prior surgery, prior-radiation therapy, and prior anticancer therapy will be listed.

6.3.4.2. Concomitant Medication and Therapy

Medications started prior to the first dose of study drug and continued into the treatment period are considered as concomitant medications and therapies. Medications taken on or after the first dose of study drug through 30 days after the last dose of study drug are considered as concomitant medications and therapies.

Concomitant medications will be coded with World Health Organization (WHO) Drug Dictionary (most up-to-date version at the time of analysis). Concomitant medications will be summarized by ATC level 2 (Therapeutic Main Group) and ATC level 4 (Chemical/Therapeutic Subgroup) for each cohort and for all patients based on All Treated Population. Medications will be sorted in

descending order of frequency of ATC level 2 and ATC level 4 within ATC level 2 in the total column. A patient will be counted only once within each level of summarization if the patient has taken a medication more than once. Agents and medications will be reported using the generic name. All concomitant medications will be listed.

In addition, the number and percentage of patients who received concomitant medications for management of hyperphosphatemia will be summarized by medication class and generic term for each cohort and for all patients. Total duration of medications (excluding overlaps) for management of hyperphosphatemia will be also summarized.

6.4. Efficacy Analyses

Unless otherwise specified, all efficacy analyses will be performed based on patients in All Treated Population with centrally confirmed FGFR amplification. For Cohort 4 only, patients treated with recommended dose of TAS-120 in All Treated Population with centrally confirmed FGFR amplification will be used for efficacy analyses.

6.4.1. Primary Efficacy Analyses

The primary endpoints are ORR (Cohorts 1 and 2), CBR (Cohort 3) and 6-month PFS (Cohort 4). The description of each efficacy endpoint is provided in Table 3. Tumor assessments will be performed as per Table 1. Response assessments will be made based on Response Evaluation Criteria in Solid Tumors (RECIST 1.1) (3). The evaluation of endpoints will be based on central independent radiology review and the investigator or local radiologist.

Table 3: Efficacy Endpoint Definitions

Endpoint	Definition
ORR	The percentage of patients with a confirmed response of either
	CR or PR
CBR	The percentage of patients with a confirmed response of CR or
	PR or SD lasting at least 24 weeks (Cohorts 1, 2 and 4)
	The percentage of patients with a confirmed response of CR or
	SD lasting at least 24 weeks (Cohort 3)
PFS	The time from the day of first dose to the date of first
	objectively documented disease progression or death (any
	cause), whichever occurs first
6-month PFS	The percentage of patients who remain alive and progression
	free at 6 months
DOR	The time from the first documentation of response (CR or PR)
	to the first documentation of objective tumor progression or
	death due to any cause, whichever occurs first
OS	The time from the date of first dose to the death date

Abbreviations: CBR=clinical benefit rate; CR=complete response; DOR=duration of response; ORR=objective response rate; OS=overall survival; PFS=progression-free survival; PR=partial response; SD=stable disease.

ORR (Cohorts 1 and 2) will be summarized by a binomial response rate for each cohort. ORR will be calculated based on the best overall response recorded from the start of treatment until

progression disease or start of subsequent new anticancer treatment. The overall response can be derived based on target lesion response, non-target lesion response and the emergence of new lesion for patients with measurable disease at baseline. Table 4 presents the rules to derive the overall response.

The best overall response, CR and PR, will be confirmed with at least 4 weeks intervals of two consecutive time points. A minimum of 6-week interval between initial treatment (first dosing date) and tumor measurement is required for SD. The confirmation rule of the best overall response is shown in Table 5.

The exact 2-sided 95% CI based on Clopper-Pearson methodology will be derived for ORR. The null hypothesis will be rejected if at least 15 responders observed out of 55 patients. If 17 responders observed out of 55 patients, the ORR is 30.9% and the 95% exact CI is (19.1%, 44.8%).

CBR (Cohort 3) will be calculated based on the best overall response. Because patients in Cohort 3 have non-measurable disease at baseline, the overall response will be derived based on non-target lesion response and/or the emergence of new lesion(s). The exact 2-sided 95% CI based on Clopper-Pearson methodology will be derived for CBR. The null hypothesis will be rejected if at least 10 patients with clinical benefit are observed out of 24 patients in Cohort 3.

The exact 2-sided 95% CI based on Clopper-Pearson methodology will be derived for 6-month PFS rate (Cohort 4). The null hypothesis will be rejected if at least 14 patients observed to remain alive and progression free at 6 months after the start of treatment out of 28 patients who are treated at recommended dose in Cohort 4.

Table 4. Overall Response Assessment with Target/Non-target Lesion and New Lesions

Target Lesions	Non-target Lesions	New Lesions	Overall Response
CR	CR	No	CR
CR	Non-CR/Non-PD or Not all evaluated	No	PR
PR	Non-PD or Not all evaluated	No	PR
SD	Non-PD or Not all evaluated	No	SD
Not all evaluated	Non-PD	No	Not evaluable
PD	Any	Yes or No	PD
Any	PD	Yes or No	PD
Any	Any	Yes	PD

Table 5. Confirmation Rules for Overall Response of PR and CR

Earlier Response	Later Response	Confirmed Response
(to be confirmed)	(confirmation)	
CR	CR	CR
CR	Not CR or missing	SD
PR	CR or PR	PR
PR	SD or PD or missing	SD
PR	SD and then PR (only one SD in between)	PR
SD	n/a – no confirmation needed	SD
PD	n/a – no confirmation needed	PD

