4.3. Determination of Sample Size

Approximately 168 patients in total may be enrolled in the study.

Please note: the patient numbers given for efficacy analysis are for the response-evaluable population, defined as the subset of treated patients who have measurable disease (or evaluable disease in Cohort 3), who have at least 1 post-baseline disease/tumor assessment, and who have centrally confirmed *FGFR* amplification. If a treated patient is not eligible for the response-evaluable population (for example, because *FGFR* amplification cannot be centrally confirmed or no post-baseline tumor assessment is available), additional patients will be enrolled to ensure the correct number of response-evaluable patients for analysis as described below.

Sample size considerations for **Cohorts 1 and 2** (primary endpoint ORR) are based on a 2-stage Optimal Simon design, comparing a poor response of \leq 15% versus a promising response of \geq 30%, at an approximate 5% 1-sided significance level and 80% power.

- In Stage 1 (futility assessment), enrollment will include 19 patients in each cohort and accrual will continue to Stage 2, if at least 4 (21%) of 19 patients respond (CR or PR).
- In Stage 2, if the Stage 1 futility boundary is exceeded, an additional 36 patients will be enrolled, for a total of at least 55 patients per cohort. In Cohorts 1 or 2, with a total of 55 patients, if the observed ORR is 30.9%, the 95% exact confidence interval (CI) is (19.1%, 44.8%).

Sample size considerations for **Cohort 3** (primary endpoint CBR) are also based on a 2-stage Optimal Simon design. The null hypothesis that the true CBR is 25% will be tested against a 1-sided alternative, which yields a type I error rate of 5% and power of 80% when the true CBR rate is 50%. In the first stage, 9 patients will be treated. If there are \leq 2 patients with clinical benefit (ie, CR or SD \geq 24 weeks) in these 9 patients, the cohort will be discontinued. Otherwise, 15 additional patients will be treated for a total of 24 patients. The null hypothesis will be rejected if \geq 10 patients with clinical benefit are observed in 24 patients.

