6.8. Interim Analyses

The interim analyses will be performed to determine if the futility criterion was met in Cohort 1, 2 and 3, and if the particular cohort should continue. The interim analysis on Cohort 1 will be performed at the time when there are 19 response evaluable patients in Cohort 1. The interim analysis on Cohort 2 will be performed at the time when there are 19 response evaluable patients in Cohort 2. The interim analysis on Cohort 3 will be performed at the time when there are 9 response evaluable patients in Cohort 3.

During interim analyses, the sponsor will review the data and perform statistical analysis to determine if the particular cohort should continue. The interim analyses will be performed on primary efficacy endpoints only.

Because the study is powered for two-stage design (Cohort 1, 2, 3), the overall type I error is controlled for interim analysis. There is no need for type I error adjustment or sample size adjustment. Because this is open label study, there is no blinding/unblinding. Therefore there is no need for maintaining blinding during interim analysis.

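### The Cohort 1 and 2 cut-off of 15 of 55 responders does not belong to the stated Simon design, which rejects at 13, and it cuts power from 80% to 67%

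*SAP*

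**What the plan says.** SAP 4.3 and Protocol 10.1 give the same design for Cohorts 1 and 2. The sample sizes "are based on a 2-stage Optimal Simon design" with a null ORR of 15% and a target of 30%, "at an approximate 5% 1-sided significance level and 80% power". Accrual continues past stage 1 "if at least 4 (21%) of 19 patients respond (CR or PR"), after which "an additional 36 patients will be enrolled, for a total of at least 55 patients per cohort". Neither section gives a final rejection count for these two cohorts.

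The count appears only in SAP 6.4.1: "The null hypothesis will be rejected if at least 15 responders observed out of 55 patients". The next sentence there illustrates precision with 17 of 55 (30.9%, exact 95% CI 19.1% to 44.8%).

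SAP 6.8 relies on the design for error control: "Because the study is powered for two-stage design (Cohort 1, 2, 3), the overall type I error is controlled for interim analysis". SAP 7 reports no changes to the planned analyses, and nothing in either document explains a final rule stricter than the design's own.

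**The concern.** A Simon design is a set of four numbers: stage 1 size, stage 1 boundary, total size and final boundary. Its alpha and power belong to the set as a whole. If the final boundary is replaced, the stated alpha and power no longer apply.

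Here three of the four numbers are those of the stated optimal design and the fourth is not. The fourth is the decision rule for the primary endpoint in two of the four cohorts. If the drug truly reaches the 30% target, the chance of missing it rises from the planned 20% to about 33% per cohort. If a cohort ended with 13 or 14 responders, one reader could call it positive from the design section and another negative from the analysis section. In an open-label study that ambiguity cannot be resolved credibly once the data are known.

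**Working it through.** **Inputs** (SAP 4.3 and Protocol 10.1, except the last)
- Null rate p0 = 0.15, target rate p1 = 0.30
- One-sided alpha about 0.05, power 0.80
- Stage 1: n1 = 19, continue if X1 ≥ 4
- Stage 2: n2 = 36, total n = 55
- Final cut-off r = 15 (SAP 6.4.1)

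**Step 1: reproduce the stated design.** Search all two-stage designs with alpha ≤ 0.05 at p0 and power ≥ 0.80 at p1, and take the one with the smallest expected sample size under p0. The optimum has n1 = 19, stop at 3 or fewer, n = 55, and no rejection at 12 or fewer, so rejection at 13 or more.

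The probability of continuing is P(X1 ≥ 4) = 0.316 at p = 0.15 and 0.867 at p = 0.30. Expected size under p0 is 19 + 36 × 0.316 = 30.4. The stage sizes and futility rule match the documents exactly.

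**Step 2: operating characteristics by final cut-off.** With cut-off r,

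P(reject | p) = Σ over x = 4,…,19 of P(X1 = x | 19, p) × P(X2 ≥ r − x | 36, p).

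| Reject if at least | Alpha (p = 0.15) | Power (p = 0.30) |
|---|---|---|
| 13 of 55 | 0.0477 | 0.8006 |
| 14 of 55 | 0.0250 | 0.7471 |
| 15 of 55 | 0.0119 | 0.6723 |

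Only 13 gives both stated properties. The power lost by using 15 is 0.8006 − 0.6723 = 0.128.

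**Step 3: can another reading rescue 15?** If stage 1 is ignored and 55 patients are treated as a single stage, 15 or more gives alpha 0.0135 and power 0.7173, still well short of 80%. Under the two-stage rule with 15, power reaches 80% only at a true ORR of about 32.7%.

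**Step 4: where 15 may come from (inference).** Two-sided 95% Clopper-Pearson lower limits are:
- 13/55: 13.2%
- 14/55: 14.7%
- 15/55: 16.1%

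So 15 is the smallest count whose interval excludes 15%. That is a criterion of at most 2.5% one-sided, not the stated 5%. The SAP does not apply it to Cohort 3: its rule of 10 of 24 has a lower limit of 22.1%, below the 25% null, but gives two-stage alpha 0.0485 and power 0.8055, as stated for that cohort. As a check on the method, 17/55 reproduces the SAP's interval of 19.1% to 44.8%.

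**Step 5: totals other than 55.** The documents say at least 55. With the same stage 1 rule:

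| Total | Alpha at 13 | Alpha at 14 | Power at 14 |
|---|---|---|---|
| 56 | 0.0529 | 0.0284 | 0.7631 |
| 57 | 0.0584 | 0.0320 | 0.7774 |
| 60 | 0.0763 | 0.0447 | 0.8109 |

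A cut-off of 13 therefore holds the 5% level at 55 but not above it.

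**The case against.** The best defence is that 15 is the safe direction. Alpha is 1.2%, below the 5% ceiling, so the SAP 6.8 statement that type I error is controlled remains true. The decision changes only when exactly 13 or 14 patients respond, and the stage 1 futility rule is unaffected. Protocol 10.5.2 describes the efficacy analysis as descriptive with an exact interval and names no test. All of this is correct. It limits the harm to lost power, but it does not make the 80% figure true.

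A second argument is that 15 may be deliberate, chosen so that a positive result also has a 95% interval above 15%. The Cohort 3 evidence on this is mixed. The protocol's rule for that cohort, 11 of 24, has a lower limit of 25.6% and does fit such a criterion, whereas the SAP's rule of 10 of 24 does not. The origin of 15 therefore cannot be settled from the documents. If it was deliberate, the stated alpha and power are what is wrong, and one of the two still has to change.

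The objections to a bare change to 13 also stand, as conditions on the remedy. At 13 or 14 of 55 the test would reject while the reported two-sided 95% interval still includes 15%. The cut-off of 13 exceeds 5% alpha as soon as more than 55 patients are analysed. That can happen, because SAP 6.4 bases the primary analysis on all treated patients with central confirmation, not on the 55 response-evaluable patients. The lack of a rule for other totals is equally a gap in the present text.

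**Conclusion.** The concern holds. The SAP's rejection rule for Cohorts 1 and 2 and the alpha and power stated in SAP 4.3 and Protocol 10.1 cannot both be right. With 15 of 55 the true figures are alpha 1.2% and power 67.2%, against about 5% and 80% as stated. The word approximate in the design statement does not stretch that far.

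The figures assume exactly 55 analysed patients, the stage 1 rule applied as written, and true rates of 15% and 30%. The cut-off of 13 is printed nowhere; it follows from the stated inputs. The error is conservative, so no false-positive risk arises. It needs correcting because it is the primary decision rule in two cohorts and its stated power is wrong.

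**What to change.** Choose one of two reconciliations and document that it was made before stage 2 results were seen.

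1. **Keep the stated design.** In SAP 6.4.1 change the cut-off from 15 to 13 of 55, and add the same rule to SAP 4.3 and Protocol 10.1. Attained alpha becomes 4.8% instead of 1.2%, which is the level the design states. Add a sentence saying that the test is one-sided at 5%, so the two-sided 95% interval may include 15% when the null is rejected.
2. **Keep 15 of 55.** Restate SAP 4.3 and Protocol 10.1 as one-sided alpha 1.2% and power 67%, and say why the stricter rule was chosen.

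In either case, name the population to which the count applies and give a cut-off for totals other than 55. Under option 1, for example, 14 or more holds alpha below 5% for totals of 56 to 60.

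The cost is one number in the SAP and a sentence or two in each document. No extra patients are needed.

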Sample size considerations for **Cohort 4** (primary endpoint 6-month PFS) are based on a proof-of-concept Phase 2 design, differentiating a null 6-month 25% PFS rate with a target rate of 50%. Approximately 28 patients will be treated. It has approximately 80% power to reject the null hypothesis that the true 6-month PFS rate is ≤25%, considering a 1-sided alpha (type 1 error rate) of 5%. In addition, 6-12 patients will be enrolled as a safety lead-in. The patients in the safety lead-in who are treated at the recommended Phase 2 dose will be included in the main cohort of 28 patients. Thus up to 34 patients may be enrolled for this cohort.

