6. STATISTICAL ANALYSIS

6.1. General Methods

All recorded data will be presented in listings.

The categorical data will be summarized using frequency counts and percentages of patients. The continuous data will be summarized using number of non-missing observation (n), mean, standard deviation (SD), median, minimum and maximum unless otherwise specified.

Summary tables will be presented by cohort. Data listings will be presented with patient ID and cohort.

For concomitant medications/therapy and adverse events, the cycle number is determined based on their start/onset dates. For other collected data, the cycle number is determined based on their visit dates. These data include Lab test, Physical exam, Vital signs, Height and Weight, Ophthalmological exam, ECOG, ECG, Pregnancy test, Circulating tumor DNA (ctDNA), tumor biopsies, Scheduled tumor assessment.

When there are multiple laboratory records for a scheduled visit, the one closest to the target date will be used for analysis. If there are two or more records with the same time period to the target date, the record with the latest database entry date will be used for analysis.

Time to event distribution (e.g. progression free survival, overall survival, duration of response, time to onset of AESI in a specific category, time to resolution of AESI in a specific category) will be estimated using Kaplan Meier techniques. The number of events and censorings will be reported. When appropriate, the median along with the corresponding log-log transformed 95% CI will be estimated. Rates at fixed time points will be derived from the Kaplan Meier estimate and corresponding confidence interval will be derived based on Greenwood formula for variance derivation and on log-log transformation applied on the survivor function S(t). Confidence intervals for binomial proportions, ORR, CRB, CR rate and 6-month PFS rate, will be derived using the Clopper-Pearson method.

All the analyses of efficacy, safety, and pharmacodynamics data for this study will be performed using SAS® statistical software package, Version 9.3 or a higher version.

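### Cohort 4's rejection rule of 14 of 28 gives 57% power at a one-sided alpha of 0.4%, not the stated 80% at 5%; the cut-off that fits the design is 12 of 28

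*SAP*

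**What the plan says.** Protocol 10.1 and SAP 4.3 describe the same Cohort 4 design. In the SAP it is a proof-of-concept design "differentiating a null 6-month 25% PFS rate with a target rate of 50" per cent, and "Approximately 28 patients will be treated". On the error rates it says "It has approximately 80% power to reject the null hypothesis" of a rate of 25% or less, "considering a 1-sided alpha (type 1 error rate) of 5" per cent. Neither section gives a cut-off for Cohort 4.

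The cut-off appears only in SAP 6.4.1, where the null hypothesis is rejected with "at least 14 patients observed to remain alive and progression free at 6 months after the start of treatment out of 28 patients" treated at the recommended dose. SAP 6.1 treats the endpoint as a binomial proportion: "Confidence intervals for binomial proportions, ORR, CRB, CR rate and 6-month PFS rate, will be derived using the Clopper-Pearson method". SAP section 7 reports no changes to the planned analyses.

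**The concern.** Fourteen of 28 is an observed rate of exactly 50%, the same as the target. A rule that requires the observed rate to reach the target passes only a little more than half the time when the target is true, so it cannot also have 80% power. Either the cut-off or the stated power has to be wrong.

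This is the formal test of the primary endpoint in the only combination cohort, and there is no second stage. A result of 12 or 13 of 28 would have an exact one-sided p-value of 0.029 or 0.011. It would be significant at the declared 5% level and yet not reject under the written rule. In an open-label study, settling that conflict after the results are known would be open to challenge.

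**Working it through.** **Inputs.** n = 28, null rate 0.25, target rate 0.50, one-sided alpha 5%, power about 80% (SAP 4.3, Protocol 10.1). Cut-off c = 14 (SAP 6.4.1). The endpoint is binomial with exact methods (SAP 6.1).

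**Formula.** Let X be the number alive and progression-free at 6 months among 28.

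- alpha(c) = P(X ≥ c | n = 28, p = 0.25)
- power(c) = P(X ≥ c | n = 28, p = 0.50)

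**Step 1: can the plan's own figure be reproduced?** The smallest c with alpha(c) ≤ 5% gives the test that the design text describes.

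| Cut-off | alpha (p = 0.25) | power (p = 0.50) |
|---|---|---|
| ≥ 11 | 6.79% | 90.8% |
| ≥ 12 | 2.94% | 82.8% |
| ≥ 13 | 1.12% | 71.4% |
| ≥ 14 (SAP 6.4.1) | 0.38% | 57.5% |

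Eleven exceeds 5%, so the cut-off is 12, with power 82.8%. That fairly matches about 80%. The stated sample size, alpha and power fit together at 12 of 28.

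**Step 2: the rule as written.** At p = 0.50 the distribution of X is symmetric about 14, so

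power(14) = 0.5 + 0.5 × P(X = 14) = 0.5 + 0.5 × 0.1494 = 0.5747.

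The type II error is 1 − 0.5747 = 42.5%, against 1 − 0.8275 = 17.2% at a cut-off of 12. The loss of power is 82.8 − 57.5 = 25.3 percentage points.

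**Step 3: what 14 would need.** With n = 28 and c = 14, power reaches 80% only at a true rate of about 56%. With c = 14 and a true rate of 50%, it takes 32 patients (alpha 1.6%, power 81.1%).

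**Step 4: does the confidence interval explain 14?** Lower Clopper-Pearson limits for n = 28:

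| Observed | Two-sided 95% | One-sided 95% |
|---|---|---|
| 11 | 21.5% | 23.8% |
| 12 | 24.5% | 26.9% |
| 13 | 27.5% | 30.1% |
| 14 | 30.6% | 33.3% |

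The one-sided limit passes 25% at 12. The two-sided limit, which is a stricter one-sided 2.5% test, passes it at 13. Neither leads to 14.

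**Step 5: comparison with Cohort 3.** The SAP rule there (stop at 2 or fewer of 9, reject at 10 or more of 24) has exact alpha 4.8% and power 80.5%, matching its stated 5% and 80%. In that cohort the SAP cut-off follows from the design figures; in Cohort 4 it does not.

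**The case against.** The arithmetic is not in dispute, but several limits on the point deserve a hearing.

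- **The defect is one number.** The design text in Protocol 10.1 and SAP 4.3 gives no cut-off and is correct on its own. This stands: the stated power is wrong only for the rule that SAP 6.4.1 will apply.
- **The direction is conservative.** Alpha of 0.4% lies within 5%, so no false-positive risk is added. This stands.
- **The practical consequence may be limited.** Protocol 10.5.2 says efficacy will be summarised descriptively, and no enrolment or programme decision is tied to 14 of 28. The rate and interval would be reported whatever the count. That is fair, but SAP 6.4.1 still sets an explicit rejection rule, and that rule contradicts the declared error rates.
- **Twelve has a side effect.** At 12 of 28 the two-sided 95% interval starts at 24.5%, so the test would reject while the reported interval includes 25%. This is the usual mismatch between a one-sided 5% test and a two-sided 95% interval. The SAP already accepts it in Cohort 3, where 10 of 24 rejects with a two-sided lower limit of 22.1%. It should be stated in the text.
- **The denominator may not be 28.** SAP 6.4 restricts the analysis to recommended-dose patients with centrally confirmed amplification. The cut-off for 5% is 11 at n = 26, 12 at n = 27 to 29, and 13 at n = 30. A single fixed number does not cover these cases.
- **The sponsor may want 14.** Nothing in the documents says so, and that 14 came from the target rate is only an inference. The fix therefore has to allow for it.

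**Conclusion.** The concern holds. The Cohort 4 rule in SAP 6.4.1 has a one-sided alpha of 0.38% and a power of 57.5%, against the stated 5% and about 80%. The cut-off that matches the design is 12 of 28 (alpha 2.9%, power 82.8%). No standard reading of the test or of the interval leads to 14.

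The figures assume exactly 28 patients, all classified at 6 months. If patients who are censored or missing at 6 months count as not progression-free, the power of either rule falls further. This must be corrected, because the primary test and its stated power contradict each other by more than 20 percentage points.

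**What to change.** In SAP 6.4.1, change the Cohort 4 cut-off from 14 to 12 of 28 and state the exact properties: one-sided alpha 2.9%, power 83%. Two sentences would complete it: one saying that the test is one-sided at 5% while the reported interval is two-sided 95%, so the two can disagree at 12 of 28; and one saying that if the analysed number is not 28, the cut-off is the smallest count with exact one-sided alpha of 5% or less.

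If the sponsor does intend 14, keep it and restate SAP 4.3 and Protocol 10.1 as alpha 0.4% and power 57%.

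Either route is a change of text and needs no extra patients. Moving to 12 raises the attained type I error from 0.4% to 2.9%, still below the stated 5%. The decision should be recorded before Cohort 4 outcomes are reviewed.
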